**Table 6: Hyperglycemia**

Glucose Level	Management/Next Dose for Ipatasertib
Level 1 (<8.9 mM; OR <160 mg/dL)	

• No change in dose.

• Patient should receive education on a diabetic diet.

• Consider home glucose monitoring, as per treating physician discretion.

Level 2 (≥ 8.9 mM and < 13.9 mM; OR > 160 mg/dL and < 250 mg/dL)	

• Hold* until ≤ Glucose Level 1.

• Initiate home glucose monitoring, as per treating physician discretion.

• Add or administer a higher dose of oral metformin.

• Consider endocrinology input

• If patient is already on an oral anti-diabetic medication, the dose of ipatasertib should be reduced by one dose level. Otherwise, no dose reduction required.

• If random glucose > 200 mg/dL after 2 weeks of metformin, continue metformin and consider adding sulfonylurea and titrate.

• If random glucose > 200 mg/dL after additional 1 week of metformin and sulfonylurea, consider adding basal insulin. Titrate off insulin when medically appropriate.

Level 3 (≥ 13.9 mM and < 27.8mM; OR ≥ 250 mg/dL and < 500 mg/dL) without symptoms, i.e. polyphagia, polydipsia and polyuria.)	

• Hold* until ≤ Glucose Level 1. Resume at one dose level lower**.

• Immediate endocrinology input and home glucose monitoring, as per treating physician discretion.

• Treat hyperglycemia as medically appropriate.

• Start (or increase) metformin and sulfonylurea and rapidly titrate oral agents.

• If random glucose > 200 mg/dL after additional 1 week of metformin and sulfonylurea, consider adding basal insulin. Titrate off insulin when medically appropriate.

Level 4 (≥ 27.8 mM OR ≥ 500 mg/dL) OR (≥ 13.9 mM and < 27.8mM; OR ≥ 250 mg/dL and < 500 mg/dL with symptoms, i.e.	

• Hold* until ≤ Glucose Level 1. Resume at one dose level lower or discontinue, per investigator discretion** Immediate endocrinology input.

• Treat hyperglycemia as medically appropriate.

• Start (or increase dose of) oral anti-diabetic medications (e.g., metformin).

Glucose Level	Management/Next Dose for Ipatasertib
polyphagia, polydipsia and polyuria.)	
 
Consider intravenous fluids and/or admit if hypovolemic signs/symptoms.
 
Consider appropriate clinical management of hyperglycemia per local guidelines (insulin infusion etc.).
 
If Glucose Level 4 hyperglycemia recurs, permanently discontinue ipatasertib.
 

*	Patients requiring a delay of > 4 weeks will go off protocol therapy.
**	Patients requiring > two dose reductions will go off protocol therapy.

### Rash

Ipatasertib should be permanently discontinued for rash associated with Stevens-Johnson syndrome, toxic epidermal necrolysis, or other suspected severe hypersensitivity or allergic reaction.

**Table 7: Rash**

Grade	Management/Next Dose for Ipatasertib
Grade 1	
 
No change in dose. Initiate dermatological treatment, including topical steroid moderate strength bid and oral anti-histamine, if symptomatic.
 

Grade 2	
 
Interrupt Ipatasertib until resolution to Grade ≤ 1 or the toxicity is no longer clinically significant.
 
Treat rash with topical corticosteroids.
 
Consider treatment of rash with oral corticosteroids
 

Grade 3	
 
Interrupt Ipatasertib until resolution to Grade ≤ 1 or the toxicity is no longer clinically significant.
 
Treat rash with topical and systemic corticosteroids.
 
Consider dermatological consultation.
 
If the skin toxicity resolves to Grade ≤ 1 or is no longer clinically significant within 28 days, following completion of the steroid taper, Ipatasertib may be resumed at one dose level below the previous dose
 
If recovery of the skin toxicity to Grade ≤ 1 does not occur or skin toxicity remains clinically significant continuously for 4 weeks, or Grade 3 rash recurs, permanently discontinue Ipatasertib
 

Grade 4	
 
Administration of systemic steroids (oral or intravenous) is recommended.
 
Consider dermatological consultation and skin biopsy.
 
Ipatasertib should be permanently discontinued.
 

*	Patients requiring a delay of > 4 weeks will go off protocol therapy.
**	Patients requiring > two dose reductions will go off protocol therapy.

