There are currently no FDA approved AKT inhibitors for cancer treatment. Ipatasertib is currently under investigation in phase I, II, and III clinical trials in castration resistant prostate cancer and metastatic breast cancer ([www.clinicaltrials.gov](http://www.clinicaltrials.gov)). In a three-stage study, 30 patients were enrolled in the dose-escalation (stage I) and 22 patients in the two dose expansion cohorts (11 metastatic breast cancer and 5 patients with metastatic castration-resistant prostate cancer; stage II), or all solid tumors (n=6, stage III). The most common cancers were breast cancer (n=16) or colorectal cancer (n=14), with a median of 6 prior lines of therapy (range, 1-17). Oral Ipatasertib was administered daily for 21 days followed by 7 days off (21/7 day dosing schedule) every 28 days with doses ranging from 25-800 mg. Dose limiting toxicities (DLTs) at 800 mg were asthenia and nausea. The maximum tolerated dose for Ipatasertib was 600 mg daily on a 21-day on/7-day off schedule which was used for the expansion cohorts in stage II and stage III; however, the recommended dose for further development is 400 mg daily based upon overall tolerability profile. This dose level is being evaluated in continuous daily dosing, as well as 21-day on/7-day off schedule in phase III studies, with the schedule depending on the combination therapy studied.

In 51 treated patients in the single agent study, the most common causally-related grade 2 or greater adverse events across all dose levels were as follows: diarrhea (35%), nausea (27%), asthenia (25%), hyperglycemia (10%), decreased appetite 6%, rash (6%), and vomiting (6%). Grade 3 events were diarrhea (n=4), asthenia (n=3), hypercholesterolemia (n=1), hyperglycemia (n=1), hypophosphatemia (n=1), nausea (n=1), and toxic skin eruption (n=1). No grade 4 events were observed. Timing to the first onset of diarrhea, nausea, fatigue, and rash typically occurred during cycle 1. As proof of mechanism, reduction in the substrates pGSK3 $\beta$  and pPRAS40 was demonstrated in platelet-rich plasma. In terms of exposure, Ipatasertib  $\geq$  400 mg was associated with pGSK3 $\beta$  reduction  $\geq$  80%, and even at doses  $<$  100 mg greater than 50% inhibition was observed. In addition, comparing pretreatment and on-treatment tumor biopsies, there was a reduction in pRAS40, pEBP1, pS6, and pmTOR in a dose-dependent manner, as measured by reverse phase protein array.

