NERVOUS SYSTEM DISORDERS	Dysgeusia		Dysgeusia (Gr 2)
RESPIRATORY, THORACIC AND MEDIASTINAL DISORDERS		Pneumonitis	
SKIN AND SUBCUTANEOUS TISSUE DISORDERS		Erythema multiforme	
	Rash 		Rash (Gr 2)

This table will be updated as the toxicity profile of the agent is revised. Updates will be distributed to all Principal Investigators at the time of revision. The current version can be obtained by contacting [[contact]](mailto:[contact]). Your name, the name of the investigator, the protocol and the agent should be included in the e-mail.

Rash may include rash with or without pruritus, toxic skin eruption, and rash maculo-papular.

**Adverse events reported on Ipatasertib trials, but for which there is insufficient evidence to suggest that there was a reasonable possibility that Ipatasertib caused the adverse event:**

**CARDIAC DISORDERS** - Cardiac arrest

**GASTROINTESTINAL DISORDERS** - Abdominal distension; Gastroesophageal reflux disease

**INFECTIONS AND INFESTATIONS** - Skin infection

**INVESTIGATIONS** - Alanine aminotransferase increased; Aspartate aminotransferase increased; Cholesterol high; Investigations - Other (blood insulin increased); Investigations - Other (glucose urine present)

**METABOLISM AND NUTRITION DISORDERS** - Dehydration; Hypertriglyceridemia; Hyperlipidemia; Hypocalcemia; Hypokalemia; Hypomagnesemia; Hypophosphatemia

**MUSCULOSKELETAL AND CONNECTIVE TISSUE DISORDERS** - Arthralgia; Myalgia

**NERVOUS SYSTEM DISORDERS** - Dizziness; Headache; Paresthesia

**RENAL AND URINARY DISORDERS** - Acute kidney injury; Glucosuria

**RESPIRATORY, THORACIC AND MEDIASTINAL DISORDERS** - Dyspnea

**SKIN AND SUBCUTANEOUS TISSUE DISORDERS** - Dry skin; Skin and subcutaneous tissue disorders - Other (toxic skin eruption)

**VASCULAR DISORDERS** - Hypotension; Thromboembolic event

**NOTE:** Ipatasertib in combination with other agents could cause an exacerbation of any adverse event currently known to be caused by the other agent, or the combination may result in events never previously associated with either agent.

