**Table 1: Dose Levels for Ipatasertib**

Dose Level	Daily Dose/ Route	Dispensed As	Schedule
Starting dose level: 0	400 mg, PO	2 x 200-mg tablets	Once daily continuously for each 28 day cycle
-1	300 mg, PO	1 x 200 mg tablet 1 x 100 mg tablet	Once daily continuously for each 28 day cycle
-2	200 mg, PO	1 x 200-mg tablet	Once daily continuously for each 28 day cycle

Patients requiring more than 2 dose reductions due to treatment-toxicity will be removed from treatment. Patients requiring treatment to be held for >4 weeks will be taken off treatment.

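### Table 7, Grade 3 rash: a rash that becomes clinically non-significant within 28 days but stays at Grade 2 may be re-treated under one bullet and must be permanently stopped under the next

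*Protocol*

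**What the plan says.** Three bullets in the Grade 3 row of Protocol Table 7 (Section 3.4) govern the case.

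- **Hold:** "Interrupt Ipatasertib until resolution to Grade ≤ 1 or the toxicity is no longer clinically significant". The Grade 2 row has the same wording.
- **Resume:** "If the skin toxicity resolves to Grade ≤ 1 or is no longer clinically significant within 28 days". Once the steroid taper is complete, the drug may then be restarted one dose level lower.
- **Stop:** "If recovery of the skin toxicity to Grade ≤ 1 does not occur or skin toxicity remains clinically significant continuously for 4 weeks". In that event, or if Grade 3 rash recurs, the drug is to be discontinued permanently.

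Two general limits also apply. The Table 7 footnote reads "Patients requiring a delay of > 4 weeks will go off protocol therapy", and the text under Table 1 says the same for any hold: "Patients requiring treatment to be held for >4 weeks will be taken off treatment". The Table 1 text also adds "Patients requiring more than 2 dose reductions due to treatment-toxicity will be removed from treatment".

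The rash paragraph that introduces Table 7 covers only severe cutaneous and hypersensitivity reactions. Neither it nor the footnotes say which bullet prevails.

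**The concern.** The hold and resume bullets release the patient when *either* condition is met. The matching stop rule would therefore apply only when *neither* is met. As written, it applies when *either* fails, so the two rules overlap.

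The case that matters is a first Grade 3 rash that falls to Grade 2, is judged not clinically significant with the taper complete by day 28, and is still Grade 2 at 4 weeks. This is an operative rule for withdrawing treatment. Read literally, it permanently removes a patient whom the two preceding rules would let continue at a reduced dose. A site that does resume cannot tell whether it has deviated from the protocol.

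**Working it through.** **Logic check.** The protocol states no figure to reproduce here, so the rules are set side by side. At day 28, let

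- A = rash is Grade ≤ 1
- B = rash is not clinically significant
- C = steroid taper complete and hold no longer than 4 weeks

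Resume permitted = (A or B) and C. Stop as written = (not A) or (not B).

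With C true:

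| A | B | Resume permitted | Stop as written | Both apply |
|---|---|---|---|---|
| yes | yes | yes | no | no |
| yes | no | yes | yes | **yes** |
| no | yes | yes | yes | **yes** |
| no | no | no | yes | no |

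With C false, resumption is not permitted, so no conflict arises. Both rules therefore apply in 2 of 8 states. Without the taper and 4-week limits it would be 4 of 8, so those limits halve the overlap. The states are not equally likely, and the count says nothing about frequency.

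The finding rests only on the state (not A, B, C). The other state, Grade ≤ 1 but still clinically significant, carries no weight here because the Grade 1 row requires no dose change.

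**Worked example** (assuming both clocks start at the interruption). The rash is non-significant and the taper complete on day 20; the rash is still Grade 2 on day 28. The resume bullet permits the lower dose from day 20. The hold lasted 20 days, so neither 4-week limit is triggered. On day 28 recovery to Grade ≤ 1 has not occurred, and the stop bullet calls for a permanent stop. It makes no difference whether the 4-week period governs both parts of the stop bullet or only the second: a Grade 2 rash has not reached Grade ≤ 1 on either reading.

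**Neighbouring cases are settled elsewhere.** A hold or taper beyond 4 weeks takes the patient off therapy. A recurrent Grade 3 rash is stopped by name. A patient already at 200 mg has had two reductions and has no lower level.

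**How many patients.** Inputs:

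- Section 1.1 lists the Grade 3 events among 51 treated patients in the single-agent study, ending "nausea (n=1), and toxic skin eruption (n=1"). Doses ran from 25 to 800 mg on a 21-days-on, 7-days-off schedule.
- Footnote 2 of the CAEPR (Section 3.3) counts that event as rash: "Rash may include rash with or without pruritus, toxic skin eruption, and rash maculo-papular".
- The Schema gives an accrual goal of 35.
- f = share of first Grade 3 rashes that end at non-significant Grade 2 with the taper complete within 28 days. The documents do not give f; a range is assumed.

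Rate p = 1/51 = 0.0196, exact (Clopper-Pearson) 95% CI 0.0005 to 0.1045.

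Expected conflicts = 35 × p × f. Chance of at least one = 1 − (1 − f/51)^35.

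| f | Expected, p = 1/51 | Expected, p = 0.1045 | Chance of at least one, p = 1/51 |
|---|---|---|---|
| 10% | 0.07 | 0.37 | 7% |
| 25% | 0.17 | 0.91 | 16% |
| 50% | 0.34 | 1.83 | 29% |
| 100% | 0.69 | 3.66 | – |

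At the point estimate the expected count stays below one for every f. At the upper confidence limit, f must exceed 1/(35 × 0.1045) = 27% to reach one patient.

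**Check of the repair.** With stop = (not A) and (not B), the overlap is 0 of 8. With resume tightened to A and B and C, it is also 0 of 8.

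**The case against.** The strongest reply is that the row reads naturally in sequence: hold, resume if released within 28 days, otherwise stop. The stop bullet repeats the two conditions of the resume bullet in the same order over the same period, so it looks like the *otherwise* branch. On that view the patient in the example left the hold on day 20, and the remaining non-significant Grade 2 rash already meets the release condition of the Grade 2 row. The literal reading would also leave the clinical-significance condition in the hold and resume bullets with almost no effect. Table 8 supports this view of intent: for Grade 3 pneumonitis, resuming and stopping turn on the single criterion of Grade ≤ 1, and the two rules match.

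That is probably what was meant. But the reading works only if the stop bullet's *or* is taken as *neither … nor*, which is the correction needed. The text neither says so nor exempts a patient who has already restarted.

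Two further points stand. Resumption is a permission, so a site that always stops breaches nothing, and the literal default is the cautious one. The numbers are also thin and arguably generous. The rate rests on one event at mixed doses and f is assumed. Section 1.3 reports 26 patients already accrued when breast cancer was excluded, so about 35 − 26 = 9 remained to enrol from that point. For those nine, 9 × (1/51) × f gives 0.02, 0.04 and 0.09 expected conflicts at f = 10%, 25% and 50%. Patients still on treatment would add to that, but the protocol does not say how many there are, and Section 1.1 notes that rash typically first appears in cycle 1. This lowers the expected frequency; it does not remove the contradiction.

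**Conclusion.** The Grade 3 rash row contradicts itself for one narrow group: a first Grade 3 rash that settles at a non-significant Grade 2, with the taper complete and the hold within 4 weeks. The logical mismatch is certain from the text. Its frequency is not known, and is probably fewer than one patient in this arm. That estimate assumes that the single-agent rate carries over to 400 mg given continuously and that f lies in the range shown. Sample size, response assessment and error rates are unaffected. The weight is minor, but the rule decides whether a patient is permanently taken off treatment and should be unambiguous.

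**What to change.** Reword the stop bullet in the Grade 3 row of Table 7 to agree with the hold and resume bullets and the Grade 2 row, for example: *If within 28 days the skin toxicity has neither recovered to Grade ≤ 1 nor become clinically non-significant, or if Grade 3 rash recurs, permanently discontinue Ipatasertib.* A taper or hold that runs beyond 4 weeks remains covered by the existing footnote.

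If the stricter standard is intended, leave the stop bullet as it is and change *or* to *and* in the Grade 3 hold and resume bullets.

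The preferred fix costs one sentence at the next addendum, with no additional patients, visits or procedures.

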### Pneumonitis

Pneumonitis is not known to be causally related to any of the study drugs; however, it has been observed with other drugs treating pathways similar to Ipatasertib. Every effort should be made to determine the etiology of dyspnea

and changes in pulmonary function.

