3.3 Comprehensive Adverse Events and Potential Risks list (CAEPR) for Ipatasertib (NSC 781451)

The Comprehensive Adverse Events and Potential Risks list (CAEPR) provides a single list of reported and/or potential adverse events (AE) associated with an agent using a uniform presentation of events by body system. In addition to the comprehensive list, a subset, the Specific Protocol Exceptions to Expedited Reporting (SPEER), appears in a separate column and is identified with bold and italicized text. This subset of AEs (SPEER) is a list of events that are protocol specific exceptions to expedited reporting to NCI (except as noted below). Refer to the 'CTEP, NCI Guidelines: Adverse Event Reporting Requirements' [http://ctep.cancer.gov/protocolDevelopment/electronic\\_applications/docs/aeguidelines.pdf](http://ctep.cancer.gov/protocolDevelopment/electronic_applications/docs/aeguidelines.pdf) for further clarification. Frequency is provided based on 188 patients. Below is the CAEPR for Ipatasertib.

**NOTE:** Report AEs on the SPEER **ONLY IF** they exceed the grade noted in parentheses next to the AE in the SPEER. If this CAEPR is part of a combination protocol using multiple investigational agents and has an AE listed on different SPEERs, use the lower of the grades to determine if expedited reporting is required.

Version 2.0, September 16, 2021

Adverse Events with Possible Relationship to Ipatasertib (CTCAE 5.0 Term) [n= 188]			Specific Protocol Exceptions to Expedited Reporting (SPEER)
Likely (>20%)	Less Likely (<=20%)	Rare but Serious (<3%)	
BLOOD AND LYMPHATIC SYSTEM DISORDERS			
	Anemia		
GASTROINTESTINAL DISORDERS			
	Abdominal pain		Abdominal pain (Gr 2)
Diarrhea		Colitis	Diarrhea (Gr 2) Dyspepsia (Gr 2)
	Dyspepsia		
Nausea		Mucositis oral	Nausea (Gr 2) Vomiting (Gr 2)
	Vomiting		
HEPATOBILIARY DISORDERS			
		Hepatobiliary disorders - Other (hepatotoxicity)	
GENERAL DISORDERS AND ADMINISTRATION SITE CONDITIONS			
	Fatigue		Fatigue (Gr 2)
INVESTIGATIONS			
		Neutrophil count decreased	
		Platelet count decreased	
METABOLISM AND NUTRITION DISORDERS			
	Anorexia		Anorexia (Gr 2)

Adverse Events with Possible Relationship to Ipatasertib (CTCAE 5.0 Term) [n= 188]			Specific Protocol Exceptions to Expedited Reporting (SPEER)
Likely (>20%)	Less Likely (<=20%)	Rare but Serious (<3%)	
	Hyperglycemia		Hyperglycemia (Gr 2)

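### Does the Section 3.4 statement on pneumonitis causality conflict with the Section 3.3 risk list in a way that needs a protocol change?

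*Protocol*

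**What the plan says.** Section 3.4, under Pneumonitis, opens with "Pneumonitis is not known to be causally related to any of the study drugs". The same sentence goes on to say that "it has been observed with other drugs treating pathways similar to Ipatasertib", and the next asks investigators to establish why a patient has dyspnea or altered lung function. Table 8 then gives management by grade.

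Section 3.3 describes the CAEPR as "a single list of reported and/or potential adverse events (AE) associated with an agent". Its main table is headed "Adverse Events with Possible Relationship to Ipatasertib (CTCAE 5.0 Term) [n= 188" and is introduced with "Frequency is provided based on 188 patients". Pneumonitis stands there in the Rare but Serious (<3%) column, and its cell in the expedited-reporting exceptions (SPEER) column is empty. Below the table is a second list, for events seen in ipatasertib trials with "insufficient evidence to suggest that there was a reasonable possibility that Ipatasertib caused the adverse event". Pneumonitis is not on that list; its only respiratory entry is dyspnea. Footnote 1 to the table says "This table will be updated as the toxicity profile of the agent is revised", and Section 5.1.10 sends the reader to Section 3.3 for side effects.

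**The concern.** Both sections are current text, and at first reading they give different guidance on the same serious event. Section 3.3 separates events with a possible relationship from events with too little evidence, and it puts pneumonitis in the first group. Section 3.4 appears to say that pneumonitis is known only from other agents. The sentence stands directly above the management table, where an investigator with a suspected case will look. If it led investigators to attribute cases elsewhere, the trial could under-report treatment-related pneumonitis. The sentence is also unusual within Section 3.4. Hepatotoxicity, listed in the same frequency column as "Hepatobiliary disorders - Other (hepatotoxicity", carries no such disclaimer, and the hyperglycemia text speaks of events induced by ipatasertib.

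**Working it through.** The question is one of text, so the check has two parts: whether the statements exclude each other, and whether anything in the Protocol depends on which one is read.

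**Do they exclude each other?**

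- Section 3.4 denies that causation is known. Section 3.3 asserts a possible relationship. An event can have a possible but unestablished relationship, so both can hold.
- By its own definition the CAEPR takes in potential as well as reported events. A place in the table does not show that a case occurred on ipatasertib.
- The frequency column does not show it either. With 188 patients, 0.03 × 188 = 5.64. Since 5/188 = 2.66% and 6/188 = 3.19%, the column fits any count from 0 to 5. The document gives no pneumonitis count.
- Section 1.1 lists the Grade 3 events in the single-agent study (51 treated patients) and says that there were no Grade 4 events. Pneumonitis is not among those listed. This does not exclude milder cases, but nothing there contradicts Section 3.4.
- Read to its end, the Section 3.4 sentence is a class warning followed by a call for an etiological work-up. That fits a list which includes potential risks.

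**Does any rule depend on it?**

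| Place | What triggers action | Depends on attribution to ipatasertib? |
|---|---|---|
| Table 8 (pneumonitis) | Grade, symptoms, infection ruled out, recovery, recurrence | No |
| Table 3, Grade 2 | Toxicity judged probably or definitely related | Yes, but the table heading excludes pneumonitis |
| SPEER column, Section 3.3 | Grade above the one listed | Not applicable: pneumonitis has no entry |
| Section 3.2 | General reporting rules, held in the MATCH Master Protocol | Cannot be judged from this document |

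No rule shown here would run differently if the sentence were reworded. No sample size, endpoint or analysis in the document refers to it.

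**The case for a change.** The strongest counter-argument is the structure of the CAEPR. It has a category for events with insufficient evidence, which would suit the message of Section 3.4, and pneumonitis is not in it. An investigator reading one section and an investigator reading the other could form different starting views, and one sentence would be cheap to align.

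Part of this stands: the wording is not aligned. The inference from the second list is weak, for two reasons. First, that list holds only events reported in ipatasertib trials, so a potential event not yet reported could not appear on it; absence does not show that the evidence was judged sufficient. Second, the two groups overlap. Footnote 2 includes toxic skin eruption within rash on the main table, yet toxic skin eruption is also on the insufficient-evidence list.

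The contrast with the other toxicities shows uneven drafting. Silence on causality in the hepatotoxicity text asserts nothing. The firmer wording on hyperglycemia has support elsewhere in the Protocol: Section 1.1 reports causally related hyperglycemia of Grade 2 or higher in 10% of patients, and Section 5.1.9 calls it common to the class. The document gives no comparable data for pneumonitis.

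An influence on attribution is conceivable. Attribution is made case by case, however, the paragraph itself directs a search for the cause, and Section 5.1.10 points to the maintained list for side effects.

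**Conclusion.** This is a clerical mismatch between two compatible statements, and changing it brings no demonstrable gain. No dose, hold or discontinuation rule turns on the sentence, nor does any SPEER exception, endpoint or analysis in this document. What remains is a possible nudge to individual causality judgements, for an event whose count could be anywhere from 0 to 5 in 188; its size cannot be derived.

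The conclusion rests on two assumptions: that investigators use the updated CAEPR as their reference for side effects, as Section 5.1.10 directs, and that the Master Protocol, which is not shown, contains no rule that refers back to this sentence. A sponsor who is amending the text anyway may align the sentence with Section 3.3, but the plan does not need it.
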